10.12 Expectedness

The investigators will be responsible for determining whether an adverse event (AE) is expected or unexpected. An AE will be considered unexpected if the nature, severity, or frequency of the event is not consistent with the risk information previously described for the study intervention.

10.13 Unexpected Adverse Event

An unexpected adverse event is defined by the UNC IRB as any adverse event occurring in one or more subjects participating in a research protocol, the nature, severity, or frequency of which is not consistent with either:

- the known or foreseeable risk of adverse events associated with the procedures involved in the research that are described in (a) the protocol-related documents, such as the IRB-approved research protocol, any applicable investigator brochure, and the current IRB-approved informed consent document, and (b) other relevant sources of information, such as product labeling and package inserts; or
- the expected natural progression of any underlying disease, disorder, or condition of the subject(s) experiencing the adverse event and the subject's predisposing risk factor profile for the adverse event.

10.14 Time Period and Frequency for Event Assessment and Follow-Up

The occurrence of an adverse event (AE) or serious adverse event (SAE) may come to the attention of study personnel during study visits and interviews of a study participant presenting for medical care, or upon review by a study monitor.

Only those events that are definitely related or possibly related to participation in this research study will be reported. All AEs will be captured on the appropriate case report form (CRF). Information to be collected includes event description, time of onset, clinician's assessment of severity, relationship to study device (assessed only by those with the training and authority to make a diagnosis), and time of resolution/stabilization of the event. All AEs will be followed to adequate resolution.

Any medical condition that is present at the time that the participant is screened will be considered as baseline and not reported as an AE.

Changes in the severity of an AE will be documented to allow an assessment of the duration of the event at each level of severity to be performed. AEs characterized as intermittent require documentation of onset and duration of each episode.

Events will be followed for outcome information until resolution or stabilization.

All new or worsening adverse events (AEs) will be collected for all subjects from the time of subject enrollment through study completion or termination of the clinical investigation.

10.14.1 Serious Adverse Event (SAE)

An SAE is any adverse event temporally associated with the subject's participation in research that meets any of the following criteria:

- Death;
- Is life-threatening (places the subject at immediate risk of death from the event as it occurred);
- Requires inpatient hospitalization or prolongation of existing hospitalization;*
- Results in congenital anomaly/birth defect;

- Results in a persistent or significant disability/incapacity;

Important medical events that may not result in death, be life-threatening, or require hospitalization may be considered a serious adverse drug experience when, based upon appropriate medical judgment, they may jeopardize the patient or subject and may require medical or surgical intervention to prevent one of the outcomes listed in the definition. For reporting purposes, also consider the occurrences of pregnancy as an event, which must be reported as an important medical event.

*Hospitalization for anticipated or standard of care specified procedures such as administration of chemotherapy, central line insertion, metastasis interventional therapy, resection of primary tumor, or elective surgery, will not be considered serious adverse events.

10.14.2 Adverse Event Documentation and Reporting

Research staff will maintain records of all adverse events and report them in a timely manner via completion of the Adverse Event Case Report Form. The form should be updated with any changes including updates to severity, relatedness, and resolution. Adverse events will be reported to the UNC IRB per UNC IRB reporting requirements.

Events will be described using the NCI Common Terminology Criteria for Adverse Events (CTCAE).

10.15 Amending the Protocol

Should amendments to the protocol be required, amendments will be originated and documented by the Principal Investigator at UNC. Changes only go into effect after it has been approved by appropriate regulatory IRB. Non-significant changes that do not impact subject safety or scientific integrity of the study may be communicated via protocol clarification memo in lieu of a formal amended protocol.

10.16 Privacy and Confidentiality

Participant confidentiality and privacy is strictly held in trust by the participating investigators, their staff, and the sponsor(s) and their institutions. This confidentiality is extended to cover testing and storage of biological samples and genetic tests in addition to the clinical information relating to participants. Therefore, the study protocol, documentation, data, biological specimens and all other information generated will be held in strict confidence. No information concerning the study or the data will be released to any unauthorized third party without prior written approval of the Principal Investigator.

All research activities will be conducted in as private a setting as possible.

Authorized representatives of UNC Chapel Hill, representatives of the Institutional Review Board (IRB), regulatory agencies, or funding sponsor may inspect all documents and records required to be maintained by the investigator, including but not limited to, medical records (office, clinic, or hospital) and other applicable study records for the participants in this study. The clinical study site will permit access to such records.

The study participant's contact information will be securely stored at the clinical site for internal use during the study. At the end of the study, all records will continue to be kept in a secure location for as long a period as dictated by the reviewing IRB, Institutional policies, or sponsor requirements.

Study participant research data, which is for purposes of statistical analysis and scientific reporting, will be stored at the University of North Carolina at Chapel Hill. Individual participants and their research data will be identified by a unique study identification number. The study data entry and study management systems used by the University of North Carolina at Chapel Hill will be secured and password protected. At the end of the study, all study databases will be coded and archived at the University of North Carolina at Chapel Hill. Study participant identifiers will be documented in a master list; the master list will be maintained securely by the site investigators and kept separate from the research data.

10.17 Record Retention

Study documentation includes all eCRFs, data correction forms or queries, source documents, Sponsor-Investigator correspondence, monitoring logs/letters, and regulatory documents (e.g., protocol and amendments, IRB correspondence and approval, signed patient consent forms).

Source documents include all recordings of observations or notations of clinical activities and all reports and records necessary for the evaluation and reconstruction of the clinical research study.

Government agency regulations and directives require that all study documentation pertaining to the conduct of a clinical trial must be retained by the study investigator. In the case of a study with a drug seeking regulatory approval and marketing, these documents shall be retained for at least two years after the last approval of marketing application in an International Council for Harmonisation (ICH) region. In all other cases, study documents should be kept on file until three years after the completion and final study report of this investigational study.

10.18 Criteria for Terminating the Study

The principal Investigator reserves the right to terminate the study but intends only to exercise this right for valid scientific or administrative reasons and reasons related to protection of subjects. Appropriate authorities including study funder and the IRB will be notified in writing in the event of termination.

10.19 Investigator Responsibilities and Compliance

The Principal Investigator is responsible for the conduct of the study at the site in accordance with ethical principles originating from the Declaration of Helsinki. The Principal Investigator must assure that all study site personnel, including sub-investigators and other study staff members, adhere to the study protocol and all FDA/GCP/NCI regulations and guidelines regarding clinical trials both during and after study completion.

The Principal Investigator at each institution or site will be responsible for assuring that all the required data will be collected and entered onto the Case Report Forms. Periodically, monitoring visits will be conducted and the Principal Investigator will provide access to his/her original records to permit verification of proper entry of data. At the completion of the study, all case report forms will be reviewed by the Principal Investigator and will require his/her final signature to verify the accuracy of the data.

This study will be conducted in full accordance all applicable UNC Policies and Procedures and all applicable Federal and state laws and regulations including 45 CFR 46, and the HIPAA Privacy Rule. Any episode of noncompliance will be documented.

The investigators will perform the study in accordance with this protocol, will obtain consent and assent (unless a waiver is granted), and will report unexpected problems in accordance UNC IRB Policies and Procedures and all federal requirements. Collection, recording, and reporting of data will be accurate and will ensure the privacy, health, and welfare of research subjects during and after the study.

10.20 Adherence to the Protocol

Except for an emergency situation in which proper care for the protection, safety, and well-being of the study patient requires alternative treatment, the study shall be conducted exactly as described in the IRB-approved protocol.

10.21 Emergency Modifications

Investigators may implement a deviation from, or a change of, the protocol to eliminate an immediate hazard(s) to trial subjects without prior UNC or their respective institution's IRB approval/favorable opinion.

For any such emergency modification implemented, this occurrence will be reported to a UNC's IRB as required by current UNC IRB reporting procedures.

11 PUBLICATION

Authorship of publications will abide by the criteria established by the International Committee of Medical Journal Editors: Recommendations for the Conduct, Reporting, Editing, and Publication of Scholarly Work in Medical Journals (August 2013). Procedural details including rights of review and timing will be governed by the terms listed and agreed to by both parties in a separate clinical research agreement.

12 ASSESSMENTS

12.1 Visual Analog Scale (VAS)

Date:

- -
(YYYY-MMM-DD)

Please place an “X” on the line below to indicate the worst pain you felt with administration of the [Cytosponge/Transnasal Endoscopic Procedure (TNE)/Traditional Upper Endoscopy (EGD)].

[figure not shown]
No Pain ————— **Worst pain imaginable**

Internal Use Only:

[figure not shown]
VAS score: mm
Verified by:

12.2 Procedure Preference and Acceptability Questionnaire

[figure not shown]
1. On a scale of 0-10, please rate your experience with the Cytosponge procedure:

2. On a scale of 0-10, please rate your experience with the transnasal endoscopic procedure (TNE):

3. On a scale of 0-10, please rate your experience with the traditional upper endoscopic procedure (EGD):

4. Would you be willing to repeat the Cytosponge procedure if your physician indicated it was medically necessary? Yes No

5. Would you be willing to repeat the transnasal procedure (TNE) if your physician indicated it was medically necessary? Yes No

6. Would you be willing to repeat the traditional upper endoscopic procedure (EGD) if your physician indicated it was medically necessary? Yes No

7. Which procedure would you prefer to undergo again if your physician indicated it was medically necessary? Traditional Upper Endoscopy (EGD) Cytosponge Transnasal Endoscopy (TNE)

8. What factors, if any, influenced your decision (select all that apply)?

Discomfort/Pain Time (needed for preparation) Cost Need for Sedation
 Other: Describe:

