3.2 Secondary Objective

The secondary objectives are:

Secondary objective 1: Assess patient comfort pertaining to each screening modality (Cytosponge, TNE, and EGD) using VAS acceptability score at baseline.

Secondary objective 2: Assess willingness to repeat each screening modality (Y, N) evaluated ~7 days post-EGD.

Secondary objective 3: Determine ranking of preferred screening modality (1,2,3) evaluated ~7 days post-EGD.

Secondary objective 4: Identify factors that influence preference rankings or preferred choices among the 3 methods.

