7.3.2 TNE Administration

Prior to the scheduled upper endoscopy, Transnasal Endoscopy will be performed using the neonatal (ultrathin) endoscope (Olympus America Inc). The TNE will be performed by qualified trained investigator or sub-investigators. While it would be ideal to have one provider perform all cases, in an effort to be cognizant of the patient's time and clinical workflow demands in the endoscopy units, it would be impractical to have the same operator perform all cases. Prior to the procedure, a combination of a topical decongestant (oxymetazoline hydrochloride, 0.05%, Afrin, Schering-Plough Healthcare Products, Inc., Memphis, Tennessee) and topical anesthesia with 4% lidocaine, or another topical anesthetic based on the discretion of the physician performing the procedure, will be used to anesthetize the nares and posterior pharynx. The exam will be performed with the participant in the upright position. The posterior pharynx, esophagus and proximal stomach will be examined with the Transnasal Endoscopy approach. No biopsies will be obtained. The scope will be withdrawn from the nares following completion of the exam.

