7.3.4 Visual Analog Scale

Acceptability outcomes will include a Visual Analogue Scale (VAS) of acceptability of the Cytosponge, TNE, and EGD. Also, the subject will be asked whether he/she would be willing to repeat the assay, and,

assuming similar accuracy between modalities, whether he/she would rather undergo surveillance by Cytosponge, TNE, or standard EGD with biopsies.

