7.4.2 Procedure Preference and Acceptability Questionnaire

The procedure preference and acceptability questionnaire will be completed with the subject during the follow-up phone call. This assessment collects subject preference for the Cytosponge vs. traditional upper endoscopy vs. TNE, as well as willingness to undergo the procedure again.

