9 STATISTICAL CONSIDERATIONS

9.1 Statistical Plan & Sample Size Calculation

The acceptability of each screening modality will be assessed with the Impact of Events Scale (IES) scores, and the intrusiveness and avoidance subscales. We plan to recruit 40 subjects for the study.

Since the same subject will undergo treatment with each of the screening modalities, we anticipate that the scores generated will be correlated. We assume each pair of scores will have the same correlation. For the planned analysis, each IES score will be classified as low or high. High score will be defined as total IES score >38 .²⁵ A low score will be defined as a total IES score less than or equal to 38.

To compute power, for each of the three devices we specified the proportion of high scores as well as the correlation between observations within a subject. Estimating that 1% of the subjects undergoing sedated EGD group, 5% of those undergoing Cytosponge,²⁵ and 20% of those undergoing TNE will experience a high IES score, using a correlation of 0.3, and a sample size of 40, we specified a trivariate Binomial distribution. Random data were generated from such a distribution and Fishers Exact Test was computed from the data. This was done 10,000 times. The percentage of the 10,000 trials in which the Fishers Exact Test p-value was less than 0.05 provided our power estimate of 80% for a sample size of 40.

We will compare the median IES score for each modality using Kruskal-Wallis testing as well comparing the proportion of subjects with high IES scores for each modality using Pearson's chi-square testing. For the secondary objectives:

- **Secondary objective 1:** Median VAS score will be compared between the three modalities using Kruskal-Wallis testing
- **Secondary objective 2:** The proportion of subjects willing to repeat each test will be computed.
- **Secondary objective 3:** Subjects' preferred screening modality ranked highest will be measured as proportions. The proportion of the highest ranked screening modality will be computed.
- **Secondary objective 4:** Bivariate and multinomial logistic regression analyses will be used to identify factors such as patient discomfort, sex, and EGD indication influencing screening preference among the three modalities.

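### The preference item on the questionnaire omits the similar-accuracy premise that Section 7.3.4 specifies, so stated preference may combine acceptability with perceived diagnostic value

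*Combined protocol and SAP*

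**What the plan says.** Section 7.3.4 describes the preference question as follows: "assuming similar accuracy between modalities, whether he/she would rather undergo surveillance by Cytosponge, TNE, or standard EGD with biopsies". The comparison is conditional on equal accuracy and is framed as surveillance.

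The questionnaire in Section 12.2 has one preference item, item 7: "Which procedure would you prefer to undergo again if your physician indicated it was medically necessary". Its only condition is medical necessity. Item 8 then asks what influenced the choice and offers "Discomfort/Pain Time (needed for preparation) Cost Need for Sedation" plus a free-text Other.

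Section 7.4.2 makes this questionnaire the source of the preference data: "This assessment collects subject preference for the Cytosponge vs. traditional upper endoscopy vs. TNE, as well as willingness to undergo the procedure again". The Schedule of Events (Section 4) places it at the follow-up contact.

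Two secondary objectives in Section 3.2 use the answers. Objective 3 is to "Determine ranking of preferred screening modality (1,2,3) evaluated ~7 days post-EGD", and Section 9.1 analyses it descriptively: "The proportion of the highest ranked screening modality will be computed". For objective 4, Section 9.1 plans regression to "identify factors such as patient discomfort, sex, and EGD indication influencing screening preference among the three modalities".

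The procedures differ in what they yield. EGD is the clinically indicated examination and includes biopsy (Sections 5.1, 7.3 and 7.3.3). For TNE, Section 7.3.2 states "No biopsies will be obtained".

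**The concern.** A preference stated under equal accuracy is mainly about the experience and burden of the test. A preference stated without that condition can also take in what the subject thinks the test will find. Both are legitimate quantities, but they are not the same one, and the protocol body specifies the first while the form shown collects the second.

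The difference matters because Section 2 presents the alternative tests as already shown to be effective and says that patient acceptability is what now needs to be understood. If EGD were chosen often, a reader could not tell whether subjects found it more acceptable or chose it because it was the examination that provided biopsies. Objective 4, which is meant to explain the choice, has no structured variable for that motive.

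**Working it through.** This is mainly a comparison of texts. The plan attaches no test or power figure to preference, so there is no stated figure to reproduce. The 80% power at 40 subjects in Section 9.1 concerns high IES scores and is unaffected.

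**Step 1: the two wordings.**

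| Feature | Section 7.3.4 | Section 12.2, item 7 |
|---|---|---|
| Accuracy premise | Yes, similar accuracy | None |
| Medical-necessity condition | No | Yes |
| Framed as surveillance | Yes | No |
| Biopsy mentioned | Yes, with EGD | No |

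**Step 2: whether another form carries the Section 7.3.4 question.** The VAS form (Section 12.1) asks only about worst pain. The IES form (Section 12.3) asks about distress. The Schedule of Events lists the VAS at baseline and the preference questionnaire only at follow-up. Section 3.2 places the preference ranking at about seven days. Item 7 is therefore the only preference item on the forms shown.

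**Step 3: whether the data could separate the motives.** Item 8 has four tick-boxes, none for accuracy or biopsy. The factors that Section 9.1 names as examples are discomfort, sex and EGD indication; perceived accuracy is not among them. The motive would be recorded only if a subject volunteered it under Other.

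**Step 4: scale, as an illustration.** The input from Section 9.1 is n = 40. The number of subjects k whose first choice would differ between the two wordings is an assumption.

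- Shift in a modality's share = k/40. For k = 1, 4, 6 and 8 this is 2.5, 10, 15 and 20 points.
- 95% half-width for a share near 0.5 = 1.96 × √(0.5 × 0.5 / 40) = 0.155, or about 15 points.
- Number of subjects equal to that half-width = 0.155 × 40 = 6.2.

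A shift of 4 subjects is smaller than the sampling error, and it takes 7 or more of 40 to exceed it. The interval describes sampling error only, so it would not reflect a wording effect of any size.

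**The case against.** The strongest reply is that these may be two separate questions. Section 7.3.4 sits under the baseline visit, and the questionnaire is given at follow-up. Section 7 says that the case report forms are supplied separately from the protocol, and a figure is missing above item 1 of the questionnaire, so introductory text there cannot be ruled out. This stands in part. A reader might infer that the similar-accuracy premise is never put to subjects, but the documents do not establish that. They do show that item 7 as worded lacks it and that no scheduled baseline instrument carries it.

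Second, Sections 3.2 and 9.1 do not mention equal accuracy. Overall preference is a reasonable outcome in its own right, and experience is measured separately by the IES, the VAS and the 0–10 ratings in items 1 to 3. This is correct, and it is why amending Section 7.3.4 instead would also remove the contradiction.

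Third, a reader might infer that the result is biased toward EGD, most of all in Cohort A. The documents do not support this. Nothing in them shows what subjects believe about accuracy, and Section 2 describes TNE as no less sensitive than EGD for Barrett's esophagus. The medical-necessity clause could also be read as the physician endorsing whichever test is chosen.

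Fourth, it would be too strong to say that the problem could not be addressed afterwards. Free text under Other can be coded, and choices can be set against the ratings in items 1 to 3. Both are partial remedies, because the free text is unprompted and the ratings do not measure perceived accuracy.

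**Conclusion.** The contradiction between Section 7.3.4 and item 7 is plain on the text and should be resolved. Its consequence is one of interpretation: answers to item 7 may combine acceptability with perceived diagnostic value, and objectives 3 and 4 could not cleanly separate the two. This rests on item 7 being the preference item actually used, as Sections 4 and 7.4.2 indicate, and on there being no premise in the missing figure or in forms not shown.

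The direction and size of any shift cannot be obtained from the documents, and the figures above show scale only. Nor do the documents say that the result will be reported as preference under equal accuracy; Section 9.1 says only that a proportion is computed. The outcome is secondary and descriptive, so neither the primary analysis nor the stated power changes.

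**What to change.** Put the Section 7.3.4 premise into item 7, for example: *Assuming all three tests were similarly accurate, which would you prefer to undergo again?* Add a tick-box to item 8, *Accuracy / ability to take biopsies*, so that objective 4 has a structured variable for that motive. The example drops the medical-necessity clause, which items 4 to 6 also use. If keeping the items parallel matters, the clause can stay, provided the accuracy premise is stated.

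If the form cannot be changed, remove the premise from Section 7.3.4 and state in Section 9.1 that preference is reported as including perceived accuracy.

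The cost is a small form amendment. Under Sections 10.1 and 10.15 it needs IRB approval before use. Answers collected before the change are not fully comparable with later ones and should be reported separately, which thins an already small sample of 40.
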